Attachment 2: Cardiovascular Safety – Abnormalities

	Vital Sign Parameters			
Abnormality Code	Pulse	Diastolic Blood Pressure	Systolic Blood Pressure	
Abnormalities on actual	values			
Abnormally low	≤50 bpm	≤50 mm Hg	≤90 mm Hg	
Grade 1 or mild	-	>90 mm Hg to <100 mm Hg	>140 mm Hg to <160 mm Hg	
Grade 2 or moderate	-	≥100 mm Hg to <110 mm Hg	≥160 mm Hg to <180 mm Hg	
Grade 3 or severe	-	≥110 mm Hg	≥180 mm Hg	
Abnormally high	≥120 bpm	-	-	

The following abnormalities will be defined for vital sign measurements:

The classification of AEs related to hypotension and hypertension will be done according to the WHO Toxicity Grading Scale (see also Attachment 1).

Toxicity grading for PR interval will be performed according to the Division of Aids (DAIDS) grading table for the severity of adult and pediatric adverse events version 1.0, December 2004; clarification August 2009.

Parameter	Grade 1 Mild	Grade 2 Moderate	Grade 3 Severe	Grade 4 Potentially life- threatening
Prolonged PR inter	val			
Adult >16 years	PR interval 0.20 – 0.25 sec*	PR interval >0.25 sec	Type II 2 nd degree AV block OR Ventricular pause >3.0 sec	Complete AV block

*Revised by the sponsor.

Attachment 3: Visit Schedule for Rash Management

This visit schedule summarizes the visits and assessments to be performed in case of rash. At the investigator's discretion, additional visits and assessments can be performed. Local laboratory blood sample assessments will be documented/collected as described in the text below.

	Grade 1 Rash	Grade 2 Rash	Grade 3 or 4 Rash
Day 0 ^a	 Study medication MAY be CONTINUED. Unscheduled visit (onsite) for initial rash evaluation may be performed at the investigator's discretion. Assessment of safety blood sample by local laboratory RECOMMENDED. 	 Study medication MAY be CONTINUED. Unscheduled visit (onsite) for initial rash evaluation REQUIRED. If a visit is not possible, telephone contact with the subject should take place to collect information and to give advice on the necessary measures to be taken. Assessment of safety blood sample by local laboratory RECOMMENDED. Referral to dermatologist OPTIONAL (preferably within 24 hours after onset of rash, if performed). 	 Grade 3: SMV MUST be permanently DISCONTINUED. AL-335 and ODV MAY be CONTINUED at the investigator's discretion. Close monitoring is REQUIRED to prevent progression of the rash. Grade 4: Study medication MUST be permanently DISCONTINUED. Rechallenge is NOT ALLOWED. Unscheduled visit for initial rash evaluation as soon as possible after the subject contacts the investigator to report the event REQUIRED. Assessment of safety blood sample by local laboratory REQUIRED. Referral to dermatologist REQUIRED (preferably within 24 hours after onset of rash). Biopsy REQUIRED for grade 4 rash (as soon as possible after onset of rash). Biopsy at the dermatologist's discretion for grade 3 rash.
Day 1			• Follow-up visit (on-

NCT02993250

Clinical Protocol 64294178HPC2003 Amendment 5

	Grade 1 Rash	Grade 2 Rash	Grade 3 or 4 Rash
			 site) REQUIRED. Assessment of safety blood sample by local laboratory REQUIRED.
Further Visits	 Appropriate unscheduled Follow-up Visits at the investigator's discretion until resolution of rash.^b At these visits, safety blood samples can be taken at the investigator's discretion. 	 Appropriate unscheduled Follow-up Visits at the investigator's discretion until resolution of rash.^b At these visits, safety blood samples must be taken. 	Appropriate follow-up REQUIRED until resolution of rash or until clinical stability is reached.

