- An additional midstream urine sample must be provided at screening for a urine drug screening test. Drug screening involves analysis for amphetamines, benzodiazepines, cannabinoids, opioids and cocaine.
- In case of rash, safety blood samples (mandatory blood sample for safety in case of Grade 3 or 4 rash and at the discretion of the investigator in case of Grade 1 or 2 rash) might be taken at unscheduled visits as described in Section 9.2.8.1, and are to be processed by the local laboratory. The following parameters will need to be tested: AST, ALT, sedimentation rate, complete blood cell count (including hemoglobin, hematocrit, RBC count, WBC count, platelet count, neutrophils, lymphocytes, monocytes, eosinophils, and basophils), and creatinine.
- In the event a subject develops clinical signs suggestive of muscle injury (eg, proximal weakness, myalgias), a thorough workup (eg, assessment of CK, CK muscle-brain [CK-MB] fraction, aldolase, myoglobin, calcium, phosphate, creatinine, and urinalysis) for muscle injury should be performed by a central laboratory as described in Section 9.2.8.6.

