9.2.8.1. Rash (Including Photosensitivity Conditions)

Subjects should be informed that they should contact their doctor immediately when they notice any skin reaction. The skin reaction should be evaluated in the clinic the same day (if possible) or the next day.

Photosensitivity conditions fall under the general umbrella of rash events. However, photosensitivity reactions can be differentiated from other rash events by careful history taking and general physical examination. Photosensitivity skin reactions are typically triggered by prolonged or extreme exposure to sunlight or artificial light. These reactions may present as an exaggerated sunburn reaction, usually affecting areas exposed to light (typically the face, 'V' area of the neck, extensor surfaces of the forearms, and the dorsa of the hands). Photosensitivity reactions can be prevented by avoiding excessive sun exposure and by the use of sun protection measures.

All rash events should be captured in the Adverse Event Section of the eCRF. A separate Rash Page will be completed in case of a rash event. For rash events considered as potential photosensitivity reaction, a separate Photosensitivity Page will be completed.

Monitoring of the evolution of rash (including photosensitivity reactions) will be performed based on the grade (severity) of the rash (see Attachment 3). At the discretion of the investigator, additional visits and assessments can be performed. Management of rash will take into account the protocol-defined procedures outlined in Table 3.

Discontinuation of all study drugs should be considered if a photosensitivity reaction occurs and subjects should be monitored until the reaction has resolved.

WHO Grade	Rash Definition	Investigator Action
Grade 1 Rash	erythema	May continue intake of study drugs at
(with or without pruritus) ^{a,d}		the investigator's discretion.
		Blood tests for safety (recommended) can be done at the investigator's discretion.
Grade 2 Rash (with or without pruritus) ^{b,d}	diffuse, maculopapular rash, OR dry desquamation	May continue intake of study drugs at the investigator's discretion.
		Blood tests for safety (recommended) can be done at the investigator's discretion.

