Grade 3 Rash ^d	vesiculation, moist desquamation, or ulceration OR any cutaneous event with one of the following: -elevations in AST/ALT >2×baseline value -fever >38°C or 100°F	Permanently discontinue the intake of SMV. AL-335 and ODV may be continued at the investigator's discretion. ^c Close monitoring is required to prevent progression of the rash.
	-eosinophils >1.00×10 ³ /µL -serum sicknesslike reaction	No rechallenge is allowed.
		Blood safety tests are mandatory.
		Referral to a dermatologist is required. At the discretion of the dermatologist a biopsy might be performed.
Grade 4 Rash ^d	exfoliative dermatitis, OR mucous membrane involvement, OR erythema multiforme major, OR	Permanently discontinue the intake of all study drugs.
	Stevens-Johnson Syndrome, OR necrosis requiring surgery.	No rechallenge is allowed.
		Blood safety tests are mandatory.
		Referral to a dermatologist is required.
K AOT	ansferase; ALT=alanine aminotransferase; OI	A biopsy is required.

Table 3:	Guidelines for Subjects Developing Rash Grade 1 to Grade 4
----------	--

Key: AST=aspartate aminotransferase; ALT=alanine aminotransferase; ODV=odalasvir; SMV=simeprevir; WHO=World Health Organization

^a In case the rash evolves from a Grade 1 to a higher grade, management of the rash should follow the guidelines indicated for Grade 2 or Grade 3 or 4 rash, respectively (see Attachment 3).

^b In case the rash evolves from a Grade 2 to a Grade 3 or 4 rash, management of the rash should follow the guidelines specified for Grade 3 or 4 rash (see Attachment 3).

^c Monotherapy with any of the study drugs is not allowed.

^d Determine if subject was adhering to the recommended sun-protective measures.

When safety blood samples are drawn as per the rash management guidelines, these should be processed by the local laboratory. The following parameters will need to be tested: AST, ALT, sedimentation rate, complete blood cell count (including hemoglobin, hematocrit, RBC count, WBC count, platelet count, neutrophils, lymphocytes, monocytes, eosinophils, and basophils), and creatinine. The values of the local laboratory assessments need to be transcribed in the eCRF by the study-site personnel.

NCT02993250

Clinical Protocol 64294178HPC2003 Amendment 5

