- An unscheduled visit for initial rash evaluation is required as soon as possible after the subject contacts the investigator to report the AE. If a visit is not possible, telephone contact with the subject should take place to collect information and to give advice on the necessary measures to be taken.

- Assessment of safety blood samples by the local laboratory is recommended. The values of the local laboratory assessments need to be transcribed in the eCRF by the study-site personnel.
- Referral to a dermatologist is optional but, when done, should occur preferably within 24 hours after the onset of the rash. The investigator should obtain a copy of the dermatologist's report for assessment of rash.

Unscheduled visits will also be performed after the initial rash assessment at the investigator's discretion for appropriate follow-up until resolution of the rash. At these visits, safety blood samples can be taken at the investigator's discretion. For these and all subsequent local laboratory blood sample assessments, the values of the assessments need to be transcribed in the eCRF by the study-site personnel.

The subject should be advised to contact the investigator immediately if there is any worsening of the rash, if any systemic signs or symptoms appear, or if mucosal involvement develops. If appropriate, sun protection counseling should be provided.

In case the rash evolves from a Grade 2 to a Grade 3 to 4 rash, management of the rash should follow the guidelines specified for Grade 3 to 4 rash.

Grade 3 or Grade 4 Rash

A Grade 3 rash is defined as a rash associated with:

- vesiculation, moist desquamation, or ulceration, OR
- any cutaneous event with one of the following:
 - elevations in AST/ALT >2×baseline value
 - fever $>38^{\circ}$ C or 100° F
 - eosinophils >1.00×10³/ μ L
 - serum sicknesslike reaction

Subjects will permanently discontinue SMV. AL-335 and ODV may be continued at the investigator's discretion. Close monitoring is required to prevent progression of the rash.

A Grade 4 rash is defined as:

- exfoliative dermatitis, OR
- mucous membrane involvement, OR
- erythema multiforme major, OR
- Stevens-Johnson Syndrome, OR
- necrosis requiring surgery

Subjects will permanently discontinue all study drugs. No rechallenge is allowed.

An unscheduled (on-site) visit including a safety laboratory evaluation is required for a Grade 3 or 4 rash as soon as possible after the subject contacts the investigator to report the AE.

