Assessment of safety blood samples by the local laboratory is required on the day of initial rash evaluation and the day thereafter (Days 0 and 1). The values of the local laboratory assessments need to be transcribed in the eCRF by the study-site personnel. Referral to a dermatologist is required, preferably within 24 hours after the onset of the rash. A copy of the dermatologist report should be collected by the investigator.

A biopsy may be performed at the discretion of the dermatologist for Grade 3 rash and is required in case of a Grade 4 rash as soon as possible after the onset of rash. The investigator should obtain a copy of the dermatologist's report.

Appropriate management should be undertaken and subjects should be followed until resolution of the rash or until clinical stability is reached.

A complete summary of the guidelines for rash management is given in see Attachment 3.

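### For follow-up visits after a Grade 2 rash, Sections 9.2.8.1 and 9.2.2 make the safety blood sample optional, Attachment 3 makes it compulsory, and no precedence is stated (minor)

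*Protocol*

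**What the plan says.** Section 9.2.8.1, Grade 2 rash, provides for unscheduled visits after the initial assessment, at the investigator's discretion, until the rash resolves. On sampling it says: "At these visits, safety blood samples can be taken at the investigator's discretion". The Grade 1 text of that section uses the identical sentence. Section 9.2.2 makes rash samples at unscheduled visits compulsory for Grade 3 or 4 and "at the discretion of the investigator in case of Grade 1 or 2 rash", and refers to Section 9.2.8.1 for the details.

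Attachment 3, in the row for further visits, keeps the discretionary sentence for Grade 1. In the Grade 2 column it says instead: "At these visits, safety blood samples must be taken".

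Section 9.2.8.1 refers to Attachment 3 for monitoring a rash by grade and closes with: "A complete summary of the guidelines for rash management is given in see Attachment 3".

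On content, Section 9.2.8.1 says: "The following parameters will need to be tested: AST, ALT, sedimentation rate, complete blood cell count"; the differential includes eosinophils. Grade 3 rash includes any cutaneous event accompanied by "elevations in AST/ALT >2×baseline value" or by eosinophils above 1.00×10³/µL. The consequence is: "Subjects will permanently discontinue SMV".

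**The concern.** The two instructions concern the same grade, the same visits and the same act. A site that follows Section 9.2.8.1 and draws no blood departs from Attachment 3. The texts also disagree on whether Grade 2 is handled differently from Grade 1: the body section treats them alike at follow-up, and the attachment separates them.

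The sample can decide treatment. A Grade 2 rash is a cutaneous event, so a laboratory value alone can regrade it to Grade 3 and end SMV. Safety, including laboratory results, is the primary endpoint (Section 2.1.2). How completely Grade 3 rash and SMV discontinuation are ascertained should not depend on which page a site reads.

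**Working it through.** The plan gives no figure to reproduce on this point. The check is a comparison of texts, followed by a look at how much could turn on the difference.

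**1. The texts side by side, Grade 2 rash**

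| Place | Occasion | Sample |
|---|---|---|
| Section 9.2.8.1, Grade 2 | follow-up visits | optional |
| Section 9.2.2 | unscheduled rash visits, Grade 1 or 2 | optional |
| Attachment 3, further visits | follow-up visits | compulsory |
| Section 9.2.8.1 and Attachment 3 | initial evaluation (Day 0) | recommended in both |

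The Grade 2 row of Table 3 says: "Blood tests for safety (recommended) can be done at the investigator's discretion". It does not address follow-up visits separately, so it is weak evidence on this point. The conflict is confined to follow-up visits that are actually held.

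**2. Does the document settle which text governs?** Two things favour the body text: Section 9.2.2 refers to Section 9.2.8.1, and Attachment 3 is described as a summary. On the other side, Section 9.2.8.1 sends sites to Attachment 3 for monitoring by grade, and the Table 3 footnotes send them there when a rash worsens. Neither text is given precedence.

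**3. Can the sample alone change treatment?** Yes, and at levels that the general liver rule tolerates. Take an illustrative subject with baseline ALT at 1.0×ULN. Twice baseline is 2 × 1.0 = 2.0×ULN. A value of 2.2×ULN exceeds that, so with a rash present it meets the Grade 3 rash criterion and SMV stops. In Table 5 the same value lies between 1.25 and 2.5×ULN. It is therefore a Grade 1 elevation, for which Table 6 lets all study drugs continue at the investigator's discretion.

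**4. What else would catch it?** The Time and Events Schedule has hematology and biochemistry at baseline, Weeks 1, 2, 4 and 6, Weeks 8 and 10 (Cohort 2 only), and EOT. From Week 2 the draws are nominally 14 days apart.

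- Week 2 (D12 to D16) to Week 4 (D26 to D30): shortest gap 26 − 16 = 10 days, longest 30 − 12 = 18 days.
- The other gaps between Week 4 and EOT fall within the same 10 to 18 days.
- If rash onset falls at random in a 14-day gap, the mean wait for the next draw is 14/2 = 7 days.

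Gaps before Week 2 are shorter. Sections 9.1.1 and 9.2.8.3 also allow unscheduled safety samples and visits, and Grade 3 can be reached on clinical signs alone.

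**5. How many subjects?** The document gives no rate of Grade 2 rash with a follow-up visit and no rate of missed regrading. Only any-grade rash rates are available (Section 1.3.1), and using them assumes that they transfer to this regimen:

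- SMV 150 mg + SOF: 20 × 0.045 = 0.9 (8 weeks) plus 20 × 0.080 = 1.6 (12 weeks), total 2.5 of 40.
- SMV + PegIFN/RBV: 40 × 0.218 ≈ 8.7 of 40. Placebo with PegIFN/RBV had 16.6%, so the excess is 5.2 percentage points, or 40 × 0.052 ≈ 2 of 40.

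Section 3.2 expects less rash at 75 mg. In the pooled Japanese studies overall rash incidence was lower with SMV than in the PegIFN/RBV group. The affected group is a subset of the subjects with any rash, and its size is not derivable.

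**The case against.** The strongest reply accepts the difference in wording and disputes its weight. The laboratory route to Grade 3 applies to any cutaneous event. Yet both texts leave Grade 1 sampling optional, and both only recommend the first Grade 2 sample. The protocol thus tolerates optional sampling despite this trigger. Even Attachment 3 secures nothing, because the investigator decides whether to hold a follow-up visit at all. A site that always samples satisfies both texts. Sections 9.2.8.1 and 9.2.2 both say optional, so the attachment is the outlier and correcting its one sentence would be the smaller edit. Finally, the text of footnotes a and b to Attachment 3 is not visible in the copy reviewed. Marker b stands directly before the disputed sentence. It also appears in the Grade 1 cell, so it may concern only visit duration, but a qualification cannot be excluded.

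Most of this stands, and it limits the size of the point. It does not remove the contradiction: at a Grade 2 follow-up visit that is held, one text requires a sample and the other does not.

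A reader might infer more: that the SMV stopping rule fails, that a countable number of Grade 3 rashes would be missed, or that compulsory sampling was plainly intended. The documents support none of these. Other draws and clinical signs also lead to the rule, no relevant rate is given, and nothing shows which wording was meant.

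**Conclusion.** Wrong as written, and minor. The current text contains two incompatible rules for blood sampling at Grade 2 rash follow-up visits, with no stated precedence. Because the sample can by itself regrade the rash and end SMV, sites could differ in whether a laboratory-only Grade 3 rash is found.

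The effect is small and no probability is claimed. It arises only where a follow-up visit is held, the site relies on the optional wording, and no other draw or clinical sign reveals the change. No endpoint definition, analysis or stated statistical figure is affected. The conclusion assumes that the unseen footnotes to Attachment 3 do not qualify the requirement.

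**What to change.** Apply one rule, preferably the stricter one already in Attachment 3, because the sample feeds a stopping rule. In Section 9.2.8.1 replace the Grade 2 follow-up sentence with "At these visits, safety blood samples must be taken", and in Section 9.2.2 add the matching exception for Grade 2 follow-up visits. The Day 0 recommendation can stay as it is.

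The cost is two short edits, by amendment or site clarification, and a few extra local samples in subjects who are already attending. If the sponsor intended discretion, changing the single Grade 2 sentence in Attachment 3 also removes the contradiction, with less safety benefit.
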